5.2.2 Secondary Outcome Variables (if applicable)

Secondary outcomes will assess individual components of the primary outcomes, as well as a variety of AKI best practice metrics. Secondary outcomes include:

- 14 day mortality (proportion of patients who expire within 14 days of randomization, assessed from point of randomization to date of death from any cause within 14 days of randomization)
- Inpatient mortality (assessed from point of randomization to date of death from any cause)
- 14-day dialysis (proportion of patients who receive dialysis, assessed from point of randomization to date of first documented dialysis order, within 14 days of randomization)
- Inpatient dialysis (assess from point of randomization to date of first documented dialysis order during index hospitalization)
- Discharge on dialysis (assessed as active orders for dialysis at point of discharge from index hospitalization)
- Progression to stage 2 AKI (assessed as a doubling of serum creatinine from the date of randomization to 14 days post randomization)
- Progression to stage 3 AKI (assessed as a tripling of serum creatinine from the date of randomization to 14 days post randomization)
- Duration of AKI (defined as the time in hours between AKI onset and AKI cessation during index hospitalization)
- 30 day readmission rate
- Index hospitalization cost (assessed from point of randomization to date of discharge from index hospitalization)
- Chart documentation of AKI (assessed by post-discharge ICD-10 codes)
- Proportion of best practices achieved per subject during index hospitalization, to include:
 - o Contrast administration
 - o Fluid administration
 - o Aminoglycoside administration
 - o NSAID administration/cessation
 - o ACE inhibitor administration/cessation
 - o Urinalysis order
 - o Documentation of AKI
 - o Monitoring of creatinine

- Monitoring of urine output
- Renal consult

Each metric above is binary and the outcome is reported as a composite best practice outcome representing the proportion of best practices achieved per subject.

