 - Phosphorus (BH GH L LMW YH): Once For 1 Occurrences
- Diagnostic Orders:**
 - US, RETROPERITNL ABD, LTD: STAT
 - Bladder scan: STAT, FOUR TIME A DAY SCHEDULED When?
- Nursing Orders:**
 - Intake and output: Routine, EVERY 8 HOURS SCHEDULED
 - Measure weight: Routine, DAILY SCHEDULED
- Dietary Orders:**
 - Diet Renal Non Dialysis: DIET EFFECTIVE NOW, Starting today
Safety Tray? (Suicide/Homicide/Police Custody):
Total calories:
Fat Restriction:
Protein restriction:
Sodium Restriction: 2 gm NA
Potassium Restriction: 2gm k
Phosphorus restriction: 1000 mg phos
Fluid Restriction:
Additional Restrictions:
Diet Considerations:
Texture:
Initiate Nutrition Management Protocol (Yes/No?): Yes - Initiate Protocol

Non-alert

Patients who are not selected to receive the alert will not generate an alert in the medical record, and will continue to receive standard of care.

Study Timeline

We plan to activate our targeted alert in a step-wise fashion throughout our 4 study hospitals, beginning in Yale New Haven Hospital, followed by St. Raphael's Campus, Bridgeport Hospital and Greenwich Hospital.

Staggered enrollment will allow for proper pre-trial education as well as adequate site visits, study monitoring, quality control and clinician engagement at each site as roll out begins.

Study Outcomes

Our primary outcome will be a composite of AKI progression, dialysis (hemodialysis, continuous renal replacement therapy, or peritoneal dialysis), or mortality within 14 days of randomization.

Secondary study endpoints will look at a variety of patient outcomes as well as best practice metrics, including the following:

- Inpatient mortality
- 14-day mortality
- Inpatient dialysis
- 14-day dialysis
- Discharged on dialysis
- Percent who progress to stage 2 AKI
- Percent who progress to stage 3 AKI
- AKI duration
- 30-day readmission rate
- Cost of index hospitalization
- AKI documentation
- “Best practice” outcomes: Proportion achieved per patient during index hospitalization:
 - Contrast administration
 - Fluid administration
 - Aminoglycoside administration
 - NSAID administration/cessation
 - ACEi administration/cessation
 - Urinalysis order
 - Documentation of AKI
 - Monitoring of creatinine
 - Monitoring of urine output
 - Renal consults

All investigators will be blinded to the treatment assignment until the end of the trial period.

Clinician Outreach and Engagement

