5.3.2 Eligibility Criteria/Vulnerable Populations

In order to be eligible to participate, an individual must meet all of the following:

1. Adults \geq 18 years
2. Admitted to a participating hospital
3. Has AKI as defined by creatinine criteria
 - a. 0.3 mg/dl increase in inpatient serum creatinine over 48 hours OR
 - b. 50% relative increase in inpatient serum creatinine over 7 days

An individual who meets any of the following criteria will be excluded from participation in this study:

1. Dialysis order prior to AKI onset
2. Initial creatinine \geq 4.0 mg/dl
3. Prior admission in which patient was randomized
4. Admission to hospice service or comfort measures only order
5. ESKD diagnosis code
6. Kidney transplant within six months
7. Enrollment in another research study
8. Opted out of electronic health record research (based on screening by our best practice alert developed with Yale's Joint Data Analytics Team (JDAT))

6 Methods

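### The best-practice items are counted during the index hospitalization with no start at randomization, so care given before any alert could fire can settle them and shrink the differences between groups

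*Combined protocol and SAP*

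**What the plan says.** Section 5.2.2 lists the secondary outcomes. The best-practice outcome is "Proportion of best practices achieved per subject during index hospitalization, to include" ten items: contrast, fluids, aminoglycosides, NSAIDs, ACE inhibitors, urinalysis, documentation of AKI, monitoring of creatinine, monitoring of urine output, and renal consult. On scoring it says: "Each metric above is binary and the outcome is reported as a composite best practice outcome". The Study Outcomes part of section 5.1 gives the same window: "Proportion achieved per patient during index hospitalization".

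Other outcomes in the 5.2.2 list name randomization as their start. Cost is defined as "Index hospitalization cost (assessed from point of randomization to date of discharge from index hospitalization", and inpatient dialysis is defined as "assess from point of randomization to date of first documented dialysis order during index hospitalization". Both mortality outcomes and 14-day dialysis also start at randomization.

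Sections 5.1 and 6.1.3 place randomization at the moment the alert build finds a patient eligible. Eligibility under 5.3.2 needs a rise in inpatient creatinine: "0.3 mg/dl increase in inpatient serum creatinine over 48 hours OR" a 50% rise over 7 days. Section 4.3 makes improvement in best-practice rates the secondary objective.

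**The concern.** Every participant has spent time in hospital before assignment, because the entry criterion is a change between inpatient creatinine values. As written, the window includes that time. If an item was settled then, neither the alert nor the randomized arm could have influenced it, yet it enters the score.

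This composite is the main measure of the secondary objective. If a sizeable share of items is settled before randomization, a small or null difference could reflect the window rather than unchanged care. Two items deserve particular attention. Section 2.1 reports that the group's earlier alert trial changed measurement of creatinine and use of urinalysis, and both are in the composite. Urinalysis is commonly exposed to early credit, and creatinine is measured in everyone before entry.

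**Working it through.** **1. The plan's own figures.** The documents give no rate, effect size, power or pre-randomization share for the best-practice outcome, so there is no figure to reproduce. The only sample-size target is for the primary outcome (section 6.4.2): 3,410 × 1.2 = 4,092, which agrees with the stated total. Half of that, 4,092 / 2 = 2,046 per group, is used below for illustration only.

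**2. Windows side by side.**

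| Outcome (5.2.2) | Start | End |
|---|---|---|
| Mortality, inpatient and 14-day | randomization | death, within 14 days for the latter |
| Dialysis, inpatient and 14-day | randomization | first dialysis order in the index stay, or within 14 days |
| Cost | randomization | discharge |
| Ten best-practice items | not tied to randomization | index hospitalization |

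**3. Dilution of one item.** Let p be the share of patients in whom the item is settled before randomization. It is the same in both groups in expectation. Let q1 and q0 be the post-randomization rates, and assume that p is independent of later care.

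- Item scored as ever done: P = p + (1 − p)q, so the difference is (1 − p)(q1 − q0).
- Item scored as avoided throughout: P = (1 − p)(1 − q), so the difference is (1 − p)(q0 − q1). The factor is the same.

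With an assumed true difference of 10 points:

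| Assumed p | 0 | 20% | 40% | 60% | 80% |
|---|---|---|---|---|---|
| Observed difference (points) | 10 | 8 | 6 | 4 | 2 |

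**4. What this does to power.** Assume post-randomization rates of 40% and 45%, 2,046 per group, and two-sided alpha 0.05.

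| Assumed p | Whole-stay rates | Difference | Power |
|---|---|---|---|
| 0 | 40.0% v 45.0% | 5.0 points | 90% |
| 25% | 55.0% v 58.75% | 3.75 | 68% |
| 50% | 70.0% v 72.5% | 2.5 | 42% |
| 75% | 85.0% v 86.25% | 1.25 | 21% |

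A simulation of the composite shows the same pattern. It assumed six affected items with +2 points each, three items with no effect, 2,046 per group, an unstratified rank test and 400 runs per value. Power was about 74%, 47%, 29% and 14% at p = 0, 25%, 50% and 75%.

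**5. The creatinine item.** Entry needs at least two inpatient creatinine values. If any inpatient value counts, p = 100% and the difference on this item is (1 − 1) × d = 0. A constant item scales the mean difference of a ten-item score by 9/10 = 0.9. It leaves the rank-test p-value as it would be with the item dropped. What is lost is any real effect on creatinine monitoring.

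**6. Which comparison is affected.** Section 5.1 expects 51% to be alerted under the policy, so about 100 − 51 = 49% are alerted in the opposite arm. Let d1 and d0 be the alert's effects in patients for whom the policy does and does not recommend an alert. The arm difference is 0.51·d1 − 0.49·d0. For a uniform effect d it is 0.02·d, so 10 points becomes 0.2 points before any dilution. In alert versus control (section 6.5.1) the full d is in play, and there the factor (1 − p) has most to act on.

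**The case against.** The strongest objection is that the phrase may mark only the end of the window. Cost and inpatient dialysis both use index hospitalization in their definitions and still start at randomization, and item definitions could sit in Appendix A, whose content is not in the document. That reading is possible, but nothing in the text supports it for these items. Where the authors wanted a start at randomization they wrote it, and both descriptions of the composite leave it out.

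Several stronger readings are tempting and do not hold:

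- *The creatinine item is fixed by design.* It has no operational definition, and it is constant only if any inpatient value counts. The earlier trial reported a change in creatinine measurement, so the group has used a measure that can vary.
- *Documentation cannot respond because it comes from discharge codes.* The definition "Chart documentation of AKI (assessed by post-discharge ICD-10 codes" belongs to a separate outcome. Codes assigned after discharge can also still respond to the alert.
- *This is the only measure of the secondary objective.* Chart documentation of AKI is also a separate secondary outcome.
- *All pre-alert care counts as achieved.* That depends on scoring direction. Under avoidance scoring, earlier exposure counts as not achieved, which dilutes equally. Cessation needs prior exposure, so the formula does not fit those items.
- *With a corrected window, a null result would show that targeting left care unchanged.* It would not, because an average alert effect nearly cancels between the randomized arms.

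It also stands that the primary outcome is untouched, that section 6.5.2 treats secondary results as hypothesis-generating, and that pre-randomization care is balanced in expectation.

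**Conclusion.** The point holds. As written, the window credits care that no alert could have affected, and this pulls each affected item's difference toward zero by the factor (1 − p). The direction does not depend on unknown figures, but the size does. The documents give no p, and the 8, 6, 4 and 2 points are a range on an assumed 10-point effect with p independent of later care. The powers in the working rest on assumed rates as well.

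The consequence is lost sensitivity in the main measure of the secondary objective, not a false claim of benefit. It weighs most on alert versus control and less on the as-recommended versus anti-recommended contrast. The change is worth making because it is cheap, but it does not threaten the trial's primary conclusion.

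**What to change.** In sections 5.1 and 5.2.2, count every item that rests on a dated order or administration from randomization to discharge, or to 14 days after randomization if that is earlier, using EHR timestamps. Score creatinine monitoring as a new creatinine obtained after the qualifying one.

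Leave the source of the documentation item unchanged. Moving it to the problem list would add a problem, because the alert itself offers to make that entry (sections 5.1 and 6.1.1), and the item would then partly measure use of the alert's own button.

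Report the whole-stay version as a sensitivity analysis.

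The cost is protocol wording and a date filter on data already drawn from the EHR (section 7.5). Section 5.1 already uses prior exposures and tests within the current encounter as model features, so events before and after randomization can be separated. No new data or patients are needed. The downside is slightly less comparability with any earlier whole-stay definition, which the sensitivity analysis covers. Ending at discharge still leaves some dependence on length of stay, and the 14-day cap limits it.

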5.3 Study Population

Participants include adult inpatients with Acute Kidney Injury as defined by the KDIGO creatinine criteria of a 0.3 mg/dl increase over 48 hours or a 50% increase over 7 days.

5.3.1 Number of Participants

All inpatients at each study site will be screened by our best practice alert for eligibility. We will enroll 4,092 patients. Enrollment will be proportional to the number of patients meeting enrollment criteria at each hospital, which is to say we will not have specific enrollment goals by study site.

5.3.2 Eligibility Criteria/Vulnerable Populations

In order to be eligible to participate, an individual must meet all of the following:

1. Adults \geq 18 years
2. Admitted to a participating hospital
3. Has AKI as defined by creatinine criteria
 - a. 0.3 mg/dl increase in inpatient serum creatinine over 48 hours OR
 - b. 50% relative increase in inpatient serum creatinine over 7 days

An individual who meets any of the following criteria will be excluded from participation in this study:

1. Dialysis order prior to AKI onset
2. Initial creatinine \geq 4.0 mg/dl
3. Prior admission in which patient was randomized
4. Admission to hospice service or comfort measures only order
5. ESKD diagnosis code
6. Kidney transplant within six months
7. Enrollment in another research study
8. Opted out of electronic health record research (based on screening by our best practice alert developed with Yale's Joint Data Analytics Team (JDAT))

6 Methods

6.1 Treatment

6.1.1 Identity of Investigational Product

The intervention is a best practice alert built by our team in conjunction with our clinical application analyst team. This alert consists of a “pop-up” in the electronic medical record when a provider opens an eligible patient’s chart. The pop up alerts the provider to the patient’s AKI, gives recent creatinine values, and provides options to open an AKI-specific order set as well as add AKI to the patient’s problem list.

6.1.2 Dosage, Administration, Schedule

N/A

6.1.3 Method of Assignment/Randomization

Randomization will occur the moment the best practice build identifies a patient as being eligible. Randomization is achieved using a random number rule that is incorporated in the alert. This ensures that, upon meeting criteria, each patient is immediately and randomly assigned to an arm. Logic checks within the alerts ensure that once a patient is assigned to an arm, they remain on that arm for the remainder of their hospital stay.

6.1.4 Blinding and Procedures for Unblinding

Subjects will not be informed of their randomization status or participation in this trial as the trial could not be feasibly performed if subjects were told they were enrolled. We do not feel that post-facto informing of patients randomized in this trial is appropriate for several reasons. First, there is no guideline-based specific follow-up or intervention for acute kidney injury. Second, many patients may incorrectly assume that acute kidney injury is an iatrogenic condition, caused by poor medical care, when in fact it is indicative of the severity of the underlying medical condition. Finally, most patients will not be familiar with "acute kidney injury" and informing them of the presence of the condition may engender significant stress or anxiety without offering a tangible benefit.

All investigators will be blinded to treatment assignment until the end of the trial period. Care providers will not be blinded to the intervention as they are receiving the alert.

6.1.5 Packaging/Labelling

N/A

6.1.6 Storage Conditions

N/A

6.1.7 Concomitant therapy

Potential subjects will be excluded if they have a prior order for dialysis. All other therapies are permissible within this protocol.

6.1.8 Restrictions

There are no restrictions.

6.2 Assessments

6.2.1 Efficacy

Efficacy of the alerts will be assessed by data analysis towards our primary and secondary outcomes after all participants have been enrolled.

6.2.2 Safety and Pregnancy-related policy

We will conduct three interim analyses, at 25%, 50%, and 75% enrollment as described below in the statistical analysis plan.

6.2.3 Adverse Events Definition and Reporting

Definitions

Adverse event (AE) means any untoward medical occurrence associated with the use of an intervention in humans, whether or not considered intervention-related (21 CFR 312.32 (a)).

Given that this is a low-risk intervention in a population of individuals at high risk of unrelated adverse events (ie hospitalized patients with acute kidney injury), the study team will monitor for adverse effects of randomization AND adverse effects of alerting by periodic, blinded review of the following outcomes. Should significant differences in these outcomes arise, the independent DSMB will be convened to examine the results in an unblinded analysis and make their recommendations as to the continuation of the trial.

These events include:

- All inpatient deaths
- All dialysis events
- Progression to more severe AKI stages

Additionally, any comments received from providers regarding the safety or efficacy of the alert will be recorded and investigated to determine if an issue resulted in patient harm.

Relationship to Investigational Product

All AEs must have their relationship to study intervention assessed by the clinician who examines and evaluates the participant based on temporal relationship and his/her clinical judgment. The degree of certainty about causality will be graded using the categories below. In a clinical trial, the study product must always be suspect.

- Definitely Related – There is clear evidence to suggest a causal relationship, and other possible contributing factors can be ruled out. The clinical event, including an abnormal laboratory test result, occurs in a plausible time relationship to study intervention administration and cannot be explained by concurrent disease or other drugs or chemicals. The response to withdrawal of the study intervention (dechallenge) should be clinically plausible. The event must be pharmacologically or phenomenologically definitive, with use of a satisfactory rechallenge procedure if necessary.

- Probably Related – There is evidence to suggest a causal relationship, and the influence of other factors is unlikely. The clinical event, including an abnormal laboratory test result, occurs within a reasonable time after administration of the study intervention, is unlikely to be attributed to concurrent disease or other drugs or chemicals, and follows a clinically reasonable response on withdrawal (dechallenge). Rechallenge information is not required to fulfill this definition.
- Potentially Related – There is some evidence to suggest a causal relationship (e.g., the event occurred within a reasonable time after administration of the trial medication). However, other factors may have contributed to the event (e.g., the participant's clinical condition, other concomitant events). Although an AE may rate only as "possibly related" soon after discovery, it can be flagged as requiring more information and later be upgraded to "probably related" or "definitely related", as appropriate.
- Unlikely to be related – A clinical event, including an abnormal laboratory test result, whose temporal relationship to study intervention administration makes a causal relationship improbable (e.g., the event did not occur within a reasonable time after administration of the study intervention) and in which other drugs or chemicals or underlying disease provides plausible explanations (e.g., the participant's clinical condition, other concomitant treatments).
- Not Related – The AE is completely independent of study intervention administration, and/or evidence exists that the event is definitely related to another etiology. There must be an alternative, definitive etiology documented by the clinician.

Expectedness

The Principal Investigator will be responsible for determining whether an AE is expected or unexpected. An AE will be considered unexpected if the nature, severity, or frequency of the event is not consistent with the risk information previously described for the study intervention.

6.2.4 Pharmacokinetics (if applicable)

N/A

6.2.5 Biomarkers (if applicable)

N/A

6.3 Study Procedures

Eligible subjects will be automatically enrolled and randomized into our study under a waiver of informed consent. There will be no patient visits or procedures performed. Data will be unblinded and aggregated for analysis after all patients have been enrolled.

6.3.1 Study Schedule

N/A

6.3.2 Informed Consent

This study will operate under a waiver of informed consent. Due to the nature of the study, it is not feasible to consent subjects, as it would severely contaminate the exposure of interest. Patients randomized to the control arm would need to be told not to inform their provider of their participation in the trial, which would severely compromise the therapeutic relationship. The only way to avoid this would be to obtain informed consent from every patient on admission to the hospital, but given that the incidence of AKI is approximately 15% of admissions, this would be impractical and would be unnecessary for the vast majority of patients. Given that the research proposed presents no more than minimal risk to the subjects, and that no procedures are being performed that require consent outside of the research paradigm, we will request a waiver of consent from the Institutional Review Board.

